5.1 Eligibility

5.1.1 Inclusion criteria

- Patients with metastatic colorectal cancer who have progressed on, or are ineligible for standard therapy such as fluoropyrimidines, oxaliplatin, irinotecan, endothelial growth factor (VEGF) inhibitors such as bevacizumab, and anti-EGFR antibodies where appropriate, but are suitable candidates for regorafenib treatment.
- Patients with radiographically measurable biopsy-accessible disease.
- Patients who have an Eastern Cooperative Oncology Group (ECOG) performance score of 0 or 1.
- Age \geq 18 years.
- Life expectancy of at least 12 weeks (3 months).
- Subjects must be able to understand and be willing to sign the written informed consent form. Ideally, a signed informed consent form will be appropriately obtained prior to the conduct of any trial-specific procedure. However, if patients have had standard of care assessments performed within the screening period, but before the consent was signed, these will be admissible.
- Adequate bone marrow, liver and renal function as assessed by the following laboratory requirements:
 - Total bilirubin \leq 1.5 x the upper limits of normal (ULN)
 - Alanine aminotransferase (ALT) and aspartate amino-transferase (AST) \leq 2.5 x ULN (\leq 5 x ULN for subjects with liver involvement of their cancer)
 - Alkaline phosphatase limit \leq 2.5 x ULN (\leq 5 x ULN for subjects with liver involvement of their cancer)
 - Serum creatinine \leq 1.5 x the ULN
 - For subjects with liver metastases, AST and ALT \leq 5 X the upper normal limit of institution's normal range, and Non-fasting bilirubin 1.5 - 3.0 X the upper normal limit of institution's normal range are acceptable
 - As patients will undergo tissue biopsy, their international normalized ratio (INR)/ Partial thromboplastin time (PTT) has to be \leq 1.5 x ULN. In addition, a platelet count $>$ 100000 /mm³ and absolute neutrophil count (ANC) \geq 1500/mm³ is necessary.
-
- Women of childbearing potential must have a negative serum pregnancy test performed within 7 days prior to the start of study drug. Post-menopausal women (defined as no menses for at least 1 year) and surgically sterilized women are not required to undergo a pregnancy test. Subjects (men and women) of childbearing potential must agree to use adequate contraception beginning at the signing of the ICF until at least 3 months after the last dose of study drug. The definition of adequate contraception will be based on the judgment of the principal investigator or a designated associate but is generally defined as a hormonal or barrier method of birth control, or abstinence.
- Subject must be able to swallow and retain oral medication.

5.1.2 Exclusion criteria

- Previous assignment to treatment during this study. Subjects permanently withdrawn from study participation will not be allowed to re-enter study.
- Uncontrolled hypertension (systolic pressure >140 mm Hg or diastolic pressure > 90 mm Hg [NCI-CTCAE v4.0] on repeated measurement) despite optimal medical management.
- Active or clinically significant cardiac disease including:
 - Congestive heart failure – New York Heart Association (NYHA) > Class II.
 - Active coronary artery disease.
 - Cardiac arrhythmias requiring anti-arrhythmic therapy other than beta blockers or digoxin.
 - Unstable angina (anginal symptoms at rest), new-onset angina within 3 months before randomization, or myocardial infarction within 6 months before randomization.
- Evidence or history of bleeding diathesis or coagulopathy.
- Any hemorrhage or bleeding event \geq NCI CTCAE Grade 3 within 4 weeks prior to start of study medication.
- Subjects with any previously untreated or concurrent cancer that is distinct in primary site or histology from breast cancer except cervical cancer in-situ, treated basal cell carcinoma, or superficial bladder tumor. Subjects surviving a cancer that was curatively treated and without evidence of disease for more than 3 years before randomization are allowed. All cancer treatments must be completed at least 3 years prior to study entry (i.e., signature date of the informed consent form).
- Patients with pheochromocytoma.
- Known history of human immunodeficiency virus (HIV) infection or current chronic or active hepatitis B or C infection requiring treatment with antiviral therapy.
- Ongoing infection > Grade 2 NCI-CTCAE v4.0.
- Symptomatic metastatic brain or meningeal tumors. NB. If a patient does not have known or symptomatic CNS metastases at screening, then brain imaging is not required for the purpose of this trial.
- Presence of a non-healing wound, non-healing ulcer, or bone fracture.
- Renal failure requiring hemo-or peritoneal dialysis.
- Interstitial lung disease with ongoing signs and symptoms at the time of informed consent.
- Pleural effusion or ascites that causes respiratory compromise (\geq NCI-CTCAE version 4.0 Grade 2 dyspnea).
- History of organ allograft (including corneal transplant).
- Known or suspected allergy or hypersensitivity to any of the study drugs, study drug classes, or excipients of the formulations given during the course of this trial.
- Any malabsorption condition.
- Women who are pregnant or breast-feeding.
- Any condition which, in the investigator's opinion, makes the subject unsuitable for trial participation.

- Substance abuse, medical, psychological or social conditions that may interfere with the subject's participation in the study or evaluation of the study results.
- Excluded therapies and medications: See section 5.1.3.

5.1.3 Excluded therapies and medications, previous and concomitant

- Concurrent anti-cancer therapy (chemotherapy, radiation therapy, surgery, immunotherapy, biologic therapy, or tumor embolization) other than study treatment. The washout period between radiation therapy or tumor embolization is two weeks. Given the refractory nature of the study population, the washout period between study treatment and prior chemotherapy or biological therapy, will be 2 weeks prior to use of regorafenib.
- Concurrent use of another investigational drug or device therapy (i.e., outside of study treatment) during, or within 4 weeks of trial entry .
- Major surgical procedure, open biopsy, or significant traumatic injury within 28 days before start of study medication.
- Therapeutic anticoagulation with Vitamin-K antagonists (e.g., warfarin) .
 - However, prophylactic anticoagulation as described below is allowed:
 - Low dose warfarin (1 mg orally, once daily) with PT-INR $\leq 1.5 \times$ ULN is permitted. Infrequent bleeding or elevations in PT-INR have been reported in some subjects taking warfarin while on regorafenib therapy. Therefore, subjects taking concomitant warfarin should be monitored regularly for changes in PT, PT-INR or clinical bleeding episodes.
 - Prophylactic doses of heparin.
- Use of any herbal remedy (e.g. St. John's wort [*Hypericum perforatum*])

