5.2 Withdrawal of subjects from study

5.2.1 Withdrawal

Subjects **must be withdrawn from the trial** (treatment and procedures) for the following reasons:

- Subject withdraws consent from study treatment and study procedures. A subject must be removed from the trial at his/her own request or at the request of his/her legally acceptable representative. At any time during the trial and without giving reasons, a subject may decline to participate further. The subject will not suffer any disadvantage as a result.
- Pregnancy. Pregnancy will be reported as an SAE. (Note: subjects who have been withdrawn from treatment with study drug because of pregnancy should not undergo CT scans [with contrast]/MRI or bone scans while pregnant.)
- If, in the investigator's opinion, continuation of the trial would be harmful to the subject's well-being.
- Subject is lost to follow-up.
- Death.

Subjects **may be** withdrawn from the study for the following reasons:

- The subject is non-compliant with study drug, trial procedures, or both; including the use of anti-cancer therapy not prescribed by the study protocol.

- Severe allergic reaction to regorafenib (such as exfoliative erythroderma or Grade 3 or 4 hypersensitivity reaction).
- The development of a second cancer.
- Development of an intercurrent illness or situation which would, in the judgment of the investigator, significantly affect assessments of clinical status and trial endpoints.
- Deterioration of ECOG performance status to 4.
- Use of illicit drugs or other substances that may, in the opinion of the investigator, have a reasonable chance of contributing to toxicity or otherwise skewing trial result.

Any subject removed from the trial will remain under medical supervision until discharge or transfer is medically acceptable.

In all cases, the reason for withdrawal must be recorded in the CRF and in the subject's medical records.

Details for the premature termination of the study as a whole (or components thereof [e.g. centers, treatment arms, dose steps]) are provided in Section 11 (Premature termination of the study).

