- As the study requires tissue biopsies, subjects that are therapeutically treated with an agent such as warfarin or heparin will not be allowed to participate in the trial. However, patients that require anticoagulation after the biopsies are obtained can continue on the study. The following are not permitted:
- Other investigational treatment during or within 30 days before starting study treatment
- Systemic antitumor therapy, including cytotoxic therapy, signal transduction inhibitors, immunotherapy, and hormonal therapy
- Bone marrow transplant or stem cell rescue
- Subjects taking narrow therapeutic index medications should be monitored proactively (e.g. warfarin, phenytoin, quinidine, carbamazepine, Phenobarbital, cyclosporin, and digoxin). Warfarin is metabolized by the cytochrome enzyme CYP2C9 and its levels may be especially affected by regorafenib
- Use of any herbal remedy (e.g. St. John's wort [*Hypericum perforatum*])
- Please note: Patients should be seen frequently / early during treatment as per Prescribing Information
- Liver function tests should be obtained before initiation of regorafenib and monitored at least every 2 weeks during first 2 months of treatment. Thereafter liver function should be monitored monthly or more frequently as clinically indicated
- Monitor blood pressure weekly for the first 6 weeks of treatment and every cycle or more frequently as clinically indicated.

7. Detailed Study Plan

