7.2.1.3 Research Samples

Tumor biopsies will be obtained at baseline—prior to treatment initiation—and on day 14-21 of therapy (cycle 1). Peripheral blood collection for research purposes will occur at baseline, on day 14-21 of therapy (on day of tumor biopsy; cycle 1) and then on D1 of each cycle starting C3 (i.e., every 4 weeks starting cycle 3) up to 8 blood draws while taking regorafenib on study.

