7.2.1.10 Tumor Biopsies

The second tumor biopsy (at 2-3 weeks) can be waived in case of patient refusal, complications after the first biopsy or if the investigator deems the biopsy unsafe.

Tumor samples obtained at Georgetown Hospital and other sites will be collected by the staff of the biospecimen bank. Two specimens will be placed in biopsy cassettes embedded in optimal cutting temperature compound (OCT) and snap frozen within 15 min in dry ice or liquid nitrogen and subsequently stored at -80 until further use. The OCT embedded frozen core needle biopsy samples will be stored in the Georgetown University laboratory then shipped to the laboratory of [name] (George Mason University, [name]; Email: [contact]; [contact]) via FedEx medical shipment service after the last sample has been obtained or two years after the first sample has been obtained whichever occurs first. Once at George Mason University tissue-based laser capture microdissection and protein pathway activation mapping via reverse phase protein array analysis will take place. The rest of the samples will be placed in formalin and then paraffin blocks will be formed to be sent to Caris for CMI testing. Only the baseline tumor samples should be sent to Caris. Please see Appendix 14.1 for specimen requirements.

EVENTS TABLE and STUDY CALENDAR

Baseline evaluations are to be conducted within 28 days prior to start of protocol therapy. Scans and x-rays must be done ≤ 4 weeks prior to the start of therapy. Unless otherwise noted, a standard window of -1 day to + 2 days will be considered acceptable for all testing and evaluations (will not be considered study deviation). In the event that the patient's condition is deteriorating, laboratory evaluations should be repeated within 48 hours prior to initiation of the next dose of therapy.

	Screening Day -28 to -1	C1D1 & C2D1	Day 1 - 21 of every Cycle; starting C1	C1 D 14- 21	C1D14 & C2D14	Day 1 of each cycle starting cycle 2	Every 8 weeks	Disease progression or end of treatment ⁸
Informed consent	X							
Demographics	X							
Medical history	X							
Concurrent meds	X	X			X	X		X
β -HCG ¹	X							
Physical Exam	X	X			X	X		X
Vital signs	X	X			X	X		X
Height	X							
Weight	X	X			X	X		X
Performance status	X	X			X	X		X
Oral Regorafenib		X	X		X	X		
CBC with diff	X	X			X	X		X
Serum chemistries ²	X	X			X	X		X
PT/INR/PTT ⁷	X							
CEA ³	X	X				X		X

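### The 2-week chemotherapy/biologic washout is counted to first regorafenib use, not to the baseline research samples, so a compliant patient can be biopsied and bled shortly after the last prior dose

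*Combined protocol and SAP*

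**What the plan says.** **Washouts.** Section 5.1.3 gives the refractory population as its reason for a short interval and sets it as follows: "the washout period between study treatment and prior chemotherapy or biological therapy, will be 2 weeks prior to use of regorafenib". The sentence on local therapy, "The washout period between radiation therapy or tumor embolization is two weeks", names no second time point. Investigational agents have two rules. Section 5.1.3 excludes "Concurrent use of another investigational drug or device therapy (i.e., outside of study treatment) during, or within 4 weeks of trial entry", and section 6.5 prohibits "Other investigational treatment during or within 30 days before starting study treatment".

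**Baseline samples.** Section 7.2.1.3 requires the first biopsy before treatment starts and says of blood only that "Peripheral blood collection for research purposes will occur at baseline". The text introducing the events table says "Baseline evaluations are to be conducted within 28 days prior to start of protocol therapy". The table marks the research biopsy and the research serum in its screening column, Day -28 to -1.

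**Use of the samples.** Section 9.3.1 makes prediction from markers assayed at baseline the main goal and plans paired tests of change between time points. Section 4.2.1 expresses miRNA as fold change from the time 0 serum. Section 4.2.2 calculates protein and phosphoprotein change from baseline to week 2.

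**Information on prior therapy.** Section 7.2.1.2 collects dates and types of earlier anti-cancer and radiation treatment. Section 6.5 records medications taken in the 2 weeks before study start, with start and stop dates. Sections 9.3.1 and 9.3.2 name no analysis by time since prior therapy.

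**The concern.** The washout protects the first regorafenib dose. It does not protect the baseline sample, which is the measurement the study depends on most.

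Eligible patients have typically received VEGF inhibitors, cytotoxics and, where appropriate, anti-EGFR antibodies (section 5.1.1). The protein panel in section 4.2.2 includes phosphorylated VEGFR, EGFR, ERK and AKT. It is therefore plausible that a recent prior dose still influences some of the measured pathways when the sample is taken.

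Two analyses could be affected, in different ways:

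- **Change from baseline.** If a prior drug's effect is wearing off between the baseline and on-treatment samples, that recovery appears as change on regorafenib. The study has no control arm to show it.
- **Baseline prediction.** A marker that partly reflects recent therapy gains noise. It becomes a misleading predictor only if time since therapy is also related to response.

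The protocol already accepts that drug exposure at sampling matters. Section 4.1 times the second biopsy so that it is done before dose reductions, within a 7-day span (Day 14 to 21). The first biopsy of the same pair has a 28-day span and no visible condition on prior exposure.

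**Working it through.** The plan states no figure on this point, so there is none to reproduce. The check is calendar arithmetic.

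**Inputs**
- D = days from last prior dose to first regorafenib dose. For chemotherapy or a biologic, D is at least 14 (5.1.3).
- S = days from baseline sample to first dose, 1 to 28 (events table).
- Gap at sampling = D - S.

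**1. What the chemotherapy/biologic rule guarantees.** Minimum gap = 14 - S.

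| Sample day | S | Guaranteed gap (days) |
|---|---|---|
| Day -1 | 1 | 13 |
| Day -7 | 7 | 7 |
| Day -13 | 13 | 1 |
| Day -14 to -28 | 14 to 28 | none |

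Nothing is guaranteed on 28 - 13 = 15 of the 28 permitted days. The guarantee is under 7 days for S = 8 to 28, which is 21 of the 28. These are counts of calendar days, not of patients.

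**2. A compliant example.** With the last biologic on Day -21, D = 21, which satisfies the rule. A biopsy on Day -20 has a gap of 21 - 20 = 1 day. The same patient sampled on Day -7 has a gap of 21 - 7 = 14 days, with no delay to treatment.

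**3. Permitted sample days that give a gap of at least 14 days, by D.** This requires S to be at most D - 14.

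| D | Days out of 28 |
|---|---|
| 14 | 0 |
| 21 | 7 |
| 28 | 14 |
| 35 | 21 |
| 42 | 28 |

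**4. Radiation and embolization.** The figures in step 1 apply if the two weeks are counted to regorafenib. Otherwise the gap is undefined.

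**5. Investigational agents.** The term trial entry is not defined. If it means consent, as section 5.1.2 defines study entry, and consent precedes study-specific procedures (7.1), the gap is at least the larger of 28 and 30 - S. That is 29 days for S = 1 and 28 days for S = 2 to 28. Only if it means first dose does the minimum fall to 30 - S, from 29 days (S = 1) to 2 days (S = 28).

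**6. Cost of counting the full 14 days to the sample.** Assume prior therapy has ended by the time of sampling. The current minimum D is then the larger of 14 and S, and the anchored minimum is 14 + S. The added wait is S days for S up to 14 and 14 days beyond that, so at most 14. Median survival on regorafenib in section 1.2.2 is 6.4 months: 6.4 × 30.4375 = 194.8 days, and 14 / 194.8 = 7.2%.

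**The case against.** The strongest reply is that harm is possible but not shown. The documents say nothing about how long earlier drugs affect these markers or when samples are usually taken. The 14-day limit is the protocol's own washout length, not a demonstrated clearance time. The short washout is a reasoned choice for refractory patients, the study is exploratory, and its candidates go on to validation. All of this stands. It limits the weight of the point but does not close the timing gap.

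The reply also covers three stronger readings that a reader might infer:

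- **Samples taken before the last prior dose.** On a literal reading, with D = 14, Days -28 to -15 precede that dose. But 5.1.3 bars concurrent anti-cancer therapy, 6.5 does not permit "Systemic antitumor therapy, including cytotoxic therapy, signal transduction inhibitors, immunotherapy, and hormonal therapy", and 5.2.1 allows withdrawal for non-compliance, "including the use of anti-cancer therapy not prescribed by the study protocol". These provisions may prevent it, so the point does not rely on it.
- **Prior-drug and regorafenib effects that can never be told apart.** This goes too far. Treatment dates are collected, and 9.3.1 leaves statistical modelling open. An analysis by time since therapy is feasible; it is simply not named.
- **Every washout affected.** The investigational-agent rule guarantees at least 28 days if trial entry means consent, so that group is not clearly exposed.

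Finally, the opening of section 5.3 and the flowcharts at 14.3 and 14.4 are not visible in the copy reviewed. A timing rule could sit there.

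**Conclusion.** The point holds for prior chemotherapy and biologics: the visible text permits a baseline sample one day after the last dose and guarantees no gap at all from Day -14 back. For radiation and embolization the protection is the same or undefined, depending on an end point the text does not give.

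The consequence is a plausible bias of unknown size in baseline values and in change from baseline. The documents do not support a claim that the biomarker results would be invalid. A false baseline predictor would further require time since therapy to be associated with response, which nothing in the documents shows.

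The conclusion assumes that Day -k is k days before first dose and that no sampling rule sits in the parts not shown. This is an inexpensive improvement to a design choice rather than an error in the plan.

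**What to change.** 1. **Section 7.2.1.3 and the events table.** Take the baseline research blood and biopsy as close to first dose as feasible, with a target of Day -7 to -1. These days are already permitted, and the existing washout then guarantees at least 14 - 7 = 7 days after chemotherapy or a biologic. State that a missed target does not trigger a repeat biopsy.
2. **Section 9.3.1.** From the dates collected under 7.2.1.2, compute and report each patient's interval from last prior anti-cancer therapy to the baseline sample. Repeat the baseline-predictor and paired-change analyses without patients whose interval is under 14 days, or adjust for the interval. This also works for patients already sampled.

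**Cost.** No new visit, assay or data item is needed, and the washout is not lengthened. Scheduling becomes tighter, because patients fill prescriptions at retail or specialty pharmacies (6.2, 6.3) and cannot start until eligibility is confirmed (5.3.2). The sensitivity analysis will use fewer than the planned 40 patients if any fall below 14 days; how many cannot be said in advance.

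**Optional.** Counting the full 14 days to the sample would give a firmer guarantee. It is a real trade-off in this population: up to 14 more days of waiting, about 7% of the 6.4-month median survival, for a patient whose prior therapy had ended by sampling.

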5.2 Withdrawal of subjects from study

5.2.1 Withdrawal

Subjects **must be withdrawn from the trial** (treatment and procedures) for the following reasons:

- Subject withdraws consent from study treatment and study procedures. A subject must be removed from the trial at his/her own request or at the request of his/her legally acceptable representative. At any time during the trial and without giving reasons, a subject may decline to participate further. The subject will not suffer any disadvantage as a result.
- Pregnancy. Pregnancy will be reported as an SAE. (Note: subjects who have been withdrawn from treatment with study drug because of pregnancy should not undergo CT scans [with contrast]/MRI or bone scans while pregnant.)
- If, in the investigator's opinion, continuation of the trial would be harmful to the subject's well-being.
- Subject is lost to follow-up.
- Death.

Subjects **may be** withdrawn from the study for the following reasons:

- The subject is non-compliant with study drug, trial procedures, or both; including the use of anti-cancer therapy not prescribed by the study protocol.

- Severe allergic reaction to regorafenib (such as exfoliative erythroderma or Grade 3 or 4 hypersensitivity reaction).
- The development of a second cancer.
- Development of an intercurrent illness or situation which would, in the judgment of the investigator, significantly affect assessments of clinical status and trial endpoints.
- Deterioration of ECOG performance status to 4.
- Use of illicit drugs or other substances that may, in the opinion of the investigator, have a reasonable chance of contributing to toxicity or otherwise skewing trial result.

Any subject removed from the trial will remain under medical supervision until discharge or transfer is medically acceptable.

In all cases, the reason for withdrawal must be recorded in the CRF and in the subject's medical records.

Details for the premature termination of the study as a whole (or components thereof [e.g. centers, treatment arms, dose steps]) are provided in Section 11 (Premature termination of the study).

